### 5.3.4 Pooling of Sites

All sites will be pooled together for analysis purposes.

### 6 STUDY SAMPLE

Summary tables for disposition, demographics, baseline characteristics, medical history, prior and concomitant medications will be summarised by dose group.

### 6.1 DISPOSITION OF SUBJECTS

Summary statistics will tabulate the number and percentage of subjects who are screened, screen failures, randomised, received at least one dose of study treatment, who completed the study and who terminated the study early along with associated reasons. This table will also show the number and percentage of subjects who completed the first treatment period, who completed second treatment period, and who withdraw from treatment from each period along with associated reasons. The number and percentage of subjects included in each of the analysis populations will be presented. No statistical testing will be performed on these data. The number of randomised subjects in each dose group will be used as the denominator to calculate percentages. The disposition table will be based on all screened subjects.

Subject disposition data listings will be presented.

# 6.2 DEMOGRAPHICS AND BASELINE CHARACTERISTICS

Demographics (age, race, ethnicity, sex, weight (kg)) and baseline characteristics will be summarised by each dose group and overall.

The demographic and baseline characteristics table will be based on the SAS. Subject demographic data listings will be presented.

### 6.3 MEDICAL HISTORY

Medical history will be coded using the latest available version of the Medical Dictionary for Regulatory Activities (MedDRA) coding dictionary (version 26.0 [March 2023] or higher). Summary tables of the number and percentage of subjects with medical history by system organ

Page 25 of 50

class (SOC) and preferred term (PT) will be produced for subjects in the SAS. Medical history will be sorted by SOC and PT in descending order of frequency in the overall column (in case of a tie, alphabetical order will be followed). For the summary tables, a subject may appear more than once if they have more than one medical history finding coded under different SOC terms, or more than one medical history finding with a different PT under the same SOC term. However, the subject will be counted only once in the overall category (SOC).

Subject medical history listings with coded SOC and PT along with verbatim eCRF term will also be provided.

### 6.4 PRIOR AND CONCOMITANT MEDICATIONS

Prior medications are defined as medications that started and stopped before the date of first dosing with study medication. Any medication that started on the date of dosing will not be considered prior. Any medication that stopped on the date of dosing will be considered prior.

Concomitant medications are defined as all medications (excluding study treatment) started or ongoing on/after the date of first dosing with study drug. Medications started or ongoing on/after the date of first dosing in Period A or during the wash-out period will be considered as concomitant medications for Period A; Medications started or ongoing on/after the date of first dosing in Period B up to end of follow-up will be considered as concomitant medications for Period B. Partial start dates in prior and concomitant medications will be imputed with a conservative algorithm, to the first day of the month (if missing day) or the first month of the year (if missing month). Partial end dates in prior and concomitant medications will be imputed to the last day of the month (if missing day) or the last month of the year (if missing month). If the year is missing from the start date the medication will be considered to have been started before the date of Visit 1 for that subject.

Prior and concomitant medications will be coded by using the latest available Anatomical Therapeutic Chemical (ATC) Level 2 classification code and preferred drug name according to the World Health Organization Drug Dictionary (WHODrug) Global (March 2023 or higher). Prior and concomitant medications will be sorted by subject ID and then by start date.

Separate summary tables will be provided for prior and concomitant medications, presenting the number and percentage of subjects by each dose group; the summaries will be sorted by ATC Level 2 and PT in descending order of frequency in the overall column (in case of a tie, alphabetical order will be followed). For each subject, the medication will be counted only once within a given ATC level 2 and only once within a given preferred drug name level. A subject may appear more than once if he/she has more than 1 concomitant medication coded under different ATC categories; however, the subject will be counted only once in the overall category.

All medications will be listed.

### 7 EFFICACY ANALYSES

All efficacy endpoints, including responder rates, will be summarised separately for each cohort with descriptive statistics by cohort and visit as appropriate.

### 7.1 PRIMARY AND SECONDARY EFFICACY ANALYSIS

Efficacy endpoints will be summarised separately for each cohort by descriptive statistics or counts and percentages for each treatment group at each time point, as appropriate. All statistical hypothesis tests and confidence intervals will be two sided, using a type I error rate of 0.05. No adjustments for multiple comparisons will be used.

The change from baseline of parameters in Week 4 (and Week 2 where also relevant) will be summarised for each treatment group in the FAS population.

Statistical comparisons for the primary and secondary endpoints will be done separately for each cohort as described below in each subsection. For the primary endpoint and secondary endpoints that are a daily numerical or verbal rating scale, an analysis of covariance (ANCOVA) model will be used with the response variable as the change from baseline in the mean score at the timepoint of interest, and predictor variables (fixed effects) as treatment, baseline mean score for the endpoint, period and interaction effect between treatment and period. Subject will be included as a random effect. Investigation of other covariates such as age and sex and their impact on the results may be done post-hoc. Sample SAS code for the ANCOVA is provided below.

Normality of error terms may be checked with QQ plots or other methods. If normality assumptions are considered severely violated, log transformation will be attempted first to see if that fixes the issue. If the normality assumption is still violated after applying transformation, a non-parametric method (e.g., Wilcoxon signed-rank test) will be used for conducting treatment comparison between orvepitant (10 mg or 30 mg once daily) and placebo.

All efficacy data, both patient-reported scores/assessments and derived parameters, will be listed.

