- f. The use of other NK₁ antagonists (eg aprepitant, fosaprepitant, rolapitant) is not permitted for any reason from 4 weeks before the Baseline visit until completion of Visit 8
- g. Immune-suppressant drugs and systemic corticosteroids taken for co-morbidities are permitted provided the dose has been stable for at least 2 weeks before the screening visit and they are expected to be used at this dose throughout the study. Any other use is prohibited
- h. Supplemental oxygen is permitted provided it has been used for at least 2 weeks before the screening visit and is expected to be used throughout the study
- 13. Participation in any clinical research study evaluating another investigational drug or therapy within 30 days or within 5 half-lives (whichever is longer) of the investigational drug prior to Screening. If the subject was in an observational clinical study, no washout is required
- 14. Subjects who have previously received orvepitant at any time
- 15. Known allergy to any of the excipients used in the investigational medicinal product (IMP) (orvepitant or placebo tablets)
- 16. Subjects who, in the opinion of the Investigator, should not participate in the study for any other reason
- 17. Subjects who are dependent on the Sponsor, CRO or investigator for employment of education

PATIENT REPORTED OUTCOMES DEVELOPMENT AND VALIDATION

After completing Visit 7, a subgroup of patients from sites in all participating countries will be invited to take part in detailed cognitive debriefing interviews. These interviews form part of the

Protocol No.: ORV-PF-01 Final V4.0 (US) Page 9 of 85

ongoing development and validation of the patient reported outcomes being used to assess burden of cough.

burden of cough.			
STATI	STATISTICAL CONSIDERATIONS		
PLANNED SAMPLE SIZE	Assuming a common standard deviation of 2.7 for the difference between treatment periods, a sample size of 37 subjects per cohort (18-19 per sequence) has 90% power if the difference between treatments on the IPF Coughing Severity Scale is 1.5 points and assuming a two-sided type I error of 0.05, not adjusted for multiple comparisons. To allow for non-evaluable subjects/missing data, the withdrawal rate and extent of missing data will be monitored as the trial progresses and the actual sample size will be increased accordingly such that data is available for 37 evaluable subjects		

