### 2.4 TRIAL DESCRIPTION

The study will be a multi-center, double-blind, randomised, placebo-controlled 2-period crossover design. Two doses of orvepitant, 10 and 30 mg once daily, will be evaluated.

Subjects will participate in one of two cohorts (Cohort 1 [30 mg] and Cohort 2 [10 mg]). Within each cohort, subjects will be randomised to receive either orvepitant or placebo in the first treatment period (Treatment Period A) followed by the alternate treatment in Treatment Period B. There will be a wash-out period of 3 weeks between the two treatment periods. Subjects will be randomised 1:1 to each of the two treatment orders and 1:1 to each cohort.

Subjects will enter a screening period of up to 28 days to determine eligibility. Eligible subjects will be randomised at the Baseline visit and will participate in two identical 4-week treatment periods with the wash-out period between them. There will be a total of 8 visits including the Screening, Baseline and final Follow-up visits (Table 2 of the protocol).

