**Figure 1. Study Schematic** 

### 2.5 STUDY SAMPLE SIZE DETERMINATION

# 2.5.1 Estimated Sample Size

Assuming a common standard deviation of 2.7 for the difference between treatment periods, a sample size of 37 subjects per cohort has 90% power if the difference between treatments on the cough severity NRS is 1.5 points and assuming a two-sided type I error of 0.05, not adjusted for multiple comparisons. To allow for non-evaluable subjects/missing data the withdrawal rate and extent of missing data will be monitored as the trial progresses and the actual sample size will be increased accordingly such that data is available for 37 evaluable subjects.

As there have been no previous studies using NRS for cough severity the standard deviation of 2.7 was obtained based on historical data of the change in cough severity measured using VAS. A 2-week observational study has since been completed in which the standard deviation of the change from baseline in NRS was 1.45 (95% CI: 1.14 - 2.01). Using the upper bound of the 95% CI and applying an inflation factor of 1.3 (derived from the observed increase in standard deviation from week 2 to week 12 in the historical VAS study data) resulted in an estimated standard deviation of 2.6. As this is very similar to, and lower than, the standard deviation originally used in the sample size estimation the estimated sample size required was not updated.

The proposed clinically relevant improvement of 1.5 points in the IPF coughing severity scale is an initial estimate based on the findings from the qualitative interviews with IPF patients conducted during the observational study. The qualitative interviews and psychometric analyses being undertaken as part of the current study will confirm (or else amend) this change for use in future studies.

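### The only test named for the non-parametric fallback, the Wilcoxon signed-rank test, ignores period and sequence, although the primary ANCOVA adjusts for period

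*SAP*

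**What the plan says.** For the primary endpoint and the daily rating scales, SAP 7.1 specifies an ANCOVA by cohort with "predictor variables (fixed effects) as treatment, baseline mean score for the endpoint, period and interaction effect between treatment and period", and subject as a random effect.

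The same section sets out what happens if the residuals look wrong: "If normality assumptions are considered severely violated, log transformation will be attempted first to see if that fixes the issue". If that does not work, "a non-parametric method (e.g., Wilcoxon signed-rank test) will be used for conducting treatment comparison" between each orvepitant dose and placebo. Neither document names another rank method or says how period enters the fallback.

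The design is a two-sequence, two-period crossover: "Subjects will be randomised 1:1 to each of the two treatment orders and 1:1 to each cohort" (SAP 2.4). The protocol synopsis expects 18-19 evaluable subjects per sequence, and Protocol 7.4 says that subjects withdrawn after randomisation are not replaced.

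**The concern.** A signed-rank test takes each subject's orvepitant-versus-placebo difference and pools these over the two sequences. Any general difference between Period A and Period B enters with one sign in subjects who had orvepitant first and the opposite sign in those who had placebo first. With equal sequences this only adds spread, which costs power. With unequal sequences it also moves the centre of the pooled differences, so part of the period effect is read as treatment effect.

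The design gives a reason to expect some period effect. Inclusion criterion 9 requires a mean score of at least 5 (after rounding) in the second baseline week, which is essentially the week that supplies the Period A baseline (SAP 5.2.2). The Period B baseline is the week up to Visit 5 and has no threshold. Regression to the mean would therefore act on Period A change scores more than on Period B change scores, whatever the treatment.

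The fallback would supply the primary treatment comparison in the situation where the planned model is judged unsuitable. It should not lose the period adjustment that the planned model has.

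**Working it through.** **Inputs from the documents.** SAP 2.5.1 takes an SD of 2.7 for the within-subject difference and a two-sided 5% level, and states that "a sample size of 37 subjects per cohort has 90% power if the difference between treatments on the cough severity NRS is 1.5 points". The protocol synopsis adds the planned 18-19 per sequence.

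**Inputs assumed.** The size of the period effect (0 to 1.5 points), and a 22/15 split as an example of imbalance. The documents give neither.

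**Step 1: the plan's own figure.** For a paired t-test with n = 37, the non-centrality is (1.5/2.7) x sqrt(37) = 3.38, and power is 90.8%. With n = 36 it is 89.98%. So 37 is the smallest n that reaches 90%, and the stated sample size is reproduced.

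**Step 2: what each test sees.** Let d be the true treatment benefit, p the extra improvement in Period A over Period B whatever the treatment, n1 the number with orvepitant first, n2 the number with placebo first, and N = n1 + n2.

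- Benefit of orvepitant over placebo within subject: centred at d + p (orvepitant first) and d - p (placebo first).
- Pooled over sequences, as in the signed-rank test: the mean is d + p x (n1 - n2)/N, and the SD is sqrt(2.7² + p² x (1 - ((n1 - n2)/N)²)).
- Improvement in Period A minus improvement in Period B within subject: centred at p + d (orvepitant first) and p - d (placebo first). The two sequences differ by 2d, and p cancels. A rank-sum test between sequences is therefore free of the period effect, and half the shift estimates d.

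For a 1-point period effect:

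- 19/18: shift 1 x 1/37 = 0.03 points; SD sqrt(7.29 + 0.999) = 2.88.
- 22/15: shift 1 x 7/37 = 0.19 points; SD sqrt(7.29 + 0.964) = 2.87.

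**Step 3: power by simulation.** Normal errors, SD 2.7, d = 1.5, two-sided 0.05, 20,000 trials per cell. Adverse means that the larger sequence receives orvepitant in the worse period; favourable is the reverse.

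| Split | Period effect | Signed-rank | Rank-sum of period differences |
|---|---|---|---|
| 19/18 | 0 | 89.5% | 89.2% |
| 19/18 | 0.5, adverse / favourable | 88.1% / 89.5% | 89.2% / 89.2% |
| 19/18 | 1.0, adverse / favourable | 85.2% / 87.9% | 89.1% / 89.2% |
| 19/18 | 1.5, adverse | 79.8% | 89.2% |
| 22/15 | 0 | 89.6% | 88.1% |
| 22/15 | 1.0, adverse / favourable | 76.0% / 93.8% | 87.8% / 88.0% |
| 22/15 | 1.5, adverse | 62.5% | 87.8% |

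These rank-sum figures use no continuity correction; with one, the 19/18 figures are about 88%. The 93.8% is not a gain in power. It is the 0.19-point shift acting in the drug's favour.

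Type I error of the signed-rank test at a 1-point period effect is 3.6% at 19/18 (conservative) and 5.2-5.3% at 22/15. For the rank-sum test it is 4.7-5.1%.

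**Step 4: non-normal errors.** The fallback is used only when errors are clearly not normal, so the comparison was repeated with t(3) errors at the same SD (3,000 trials per cell, period effect 1.0, adverse). At 19/18, signed-rank power is 96.3% against 98.1%. At 22/15 it is 92.7% against 98.0%. The gaps are about 2 and 5 points, against about 4 and 12 with normal errors.

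**The case against.** **The SAP does not fix the test.** The signed-rank test is given as an example, so a period-adjusted rank test is not barred. This stands, and the point is limited accordingly: an open choice for the primary comparison has one named candidate, and that candidate is not the suitable one.

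**The fallback may never be used.** It needs a severe departure from normality in changes of 7-day averages, followed by a failed log transformation. The primary ANCOVA and the supportive MMRM both include period. This stands too. However, if the log were applied to the change itself, improvements would be negative, and SAP 5.1 provides only for zero values. In that case the log step would offer little protection.

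**The size of the period effect is unknown.** A reader might take the 15.8% placebo reduction in VOLCANO-2 as evidence for about 1 point. The documents do not support that. The figure is a Week 12 daytime VAS result in a parallel-group trial in refractory or unexplained chronic cough. A placebo response that recurs in Period B also cancels, because each period has its own baseline. The selection argument makes a period effect plausible but does not give its size.

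**A 22/15 split is unlikely.** Protocol 7.1 plans about 88 subjects, so 44 per cohort. If the list gives 22/22 and seven subjects are lost at random, the chance that all seven come from one sequence is 2 x C(22,7)/C(44,7) = 0.9%. Differential dropout or unblocked randomisation would raise it, but the documents give no ground for expecting either. The 22/15 row is an illustration.

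**The replacement also loses information.** The rank-sum test drops the baseline covariate and subjects with only one evaluable period, whom the mixed ANCOVA keeps. That is true, and equally true of the signed-rank test.

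**Conclusion.** The point holds as a cheap improvement to a contingency analysis. The plan adjusts for period in the main model, and the only rank test that it names does not.

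At the planned 18-19 per sequence the consequence is modest. The shift is negligible, and a 1-point period effect costs about 1 to 4 points of power depending on sign with normal errors, and about 2 with t(3) errors. With unequal evaluable sequences the estimate moves by the period effect times (n1 - n2)/N. At an assumed 22/15 split and 1 point this is 0.19 points, with rejection of about 76% or 94% against 88% for the rank-sum test under normal errors.

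Three stronger readings are not supported. The SAP does not commit the trial to the signed-rank test. It is not true that any period effect lowers the chance of a significant result, because with unequal sequences the sign decides the direction. Nor is the normal-error gap at 22/15 a forecast: it rests on an assumed split and period effect, and on an error distribution that would not normally trigger the fallback.

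**What to change.** Before unblinding, amend SAP 7.1 to replace the example with a named method: within each cohort, a Wilcoxon rank-sum test comparing within-subject period differences (Period A minus Period B in the change from baseline) between the two sequences. Report half the Hodges-Lehmann shift, signed as orvepitant minus placebo, with its 95% CI halved in the same way. This also supplies the difference and interval that SAP 7.1.1.1 promises, for which the fallback text gives no method. Apply the same rule to the secondary daily scales covered by that paragraph.

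The cost is one line of text and the matching code. If there is no period effect, the loss against the signed-rank test is 0.3 points of power at 19/18 (89.5% against 89.2%) and 1.5 points at 22/15 (89.6% against 88.1%). It grows with more extreme imbalance: at 25/12, which could not arise from 22 per sequence, it is 89.5% against 84.5%. The SAP should also state that the test uses only subjects evaluable in both periods and does not adjust for baseline.

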### 7.1.1 Primary Efficacy Endpoint

### 7.1.1.1 Main Analysis of Primary Efficacy Endpoint

The primary endpoint is the mean change from baseline to Week 4 (the average of the last 7 days before the relevant visit) in weekly average of the daily IPF Coughing Severity Scale score.

- The weekly average score is derived using NRS scores recorded in the eDiary from the last 7 calendar days up to and including the date of the relevant visit (please also refer to Section 5.3.2 for details).
- At least 4 scores are required to derive a weekly average. These four scores do not have to be on consecutive days.
- If 4 scores are not recorded in the eDiary the weekly average will be considered missing.

Change from baseline to Week 4 in weekly average of the daily IPF Coughing Severity Scale score will be analyzed using the ANCOVA model as described in Section 7.1. Least square means and corresponding 95% confidence intervals (CIs) will be presented by treatment group/cohort. Mean difference, corresponding CIs and p-value for treatment comparison between orvepitant (10 mg or 30 mg once daily) and placebo will also be presented. The mean change from baseline and the corresponding 95% confidence intervals (CIs) of the primary endpoint from the ANCOVA analysis will be displayed graphically at Week 4 by treatment group/cohort.

### 7.1.1.2 Supportive/Sensitivity Analysis of Primary Efficacy Endpoint

# Mixed Model for Repeated Measures (MMRM)

Change from baseline in weekly average of the daily IPF Coughing Severity Scale score at Week 2 and Week 4 will also be analysed using mixed model for repeated measures (MMRM). The model will include treatment, time point (Week 2 or Week 4), treatment by time point, period and treatment by period as fixed effects and subject as a random effect. Baseline will be included as a covariate. Sample SAS code for MMRM is provided below.

As measurements over time within each period are expected to be correlated, a covariance structure will be used to model the correlation. Several covariance structures will be tested, including unstructured (UN), compound symmetry (CS), 1st order autocorrelation [AR(1)]. The covariance structures with the smallest Akaike's information criterion (AICC) will be chosen and used in the model.

Least square means and corresponding 95% CIs at Week 2 and Week 4 will be presented by treatment group/cohort. Mean difference, corresponding CIs and p-value for treatment comparison between orvepitant (10 mg or 30 mg once daily) and placebo will also be presented at Week 2 and Week 4. The mean change from baseline and the corresponding 95% confidence interval (CI) will be displayed graphically by visit (Week 2 and Week 4) for the observed values and by treatment group/cohort.

